
Citation list uploaded.

2. * Describe the study hypothesis and/or research questions. Use lay language whenever possible.

The primary aim of this randomized controlled trial (RCT) is to preliminarily evaluate the efficacy of the Personalized Feedback Program (PFP) as compared to an assessment only control group, a computer-delivered intervention based on brief motivational intervention (BMI) content/principles, and a combined PFP+BMI condition.

Hypothesis 1: Students who receive the PFP will demonstrate significantly lower rates of substance use and related problems in comparison to students in the control condition and the BMI group at the 30-day and 3-month follow-ups.

Hypothesis 2: Students in the PFP+BMI condition will display significantly lower rates of substance use than students in either the PFP or BMI conditions.

3. * Describe the study's specific aims or goals. Use lay language whenever possible.

The primary aim of this proposal is to conduct a preliminary test of efficacy of our newly developed innovative prevention intervention, the Personalized Feedback Program (PFP) for college students. The PFP provides feedback about students' unique personality-related traits and how these factors relate to wellness, general college success, and substance use, along with personalized recommendations and resources. Preliminary efficacy will be evaluated through a randomized controlled trial (RCT) comparing four conditions: assessment only controls, PFP, computer-delivered intervention based on brief motivational intervention (BMI) content/principles, and PFP+BMI.

4. * Describe the scientific benefit or importance of the knowledge to be gained:

Serving the students that are part of our university community is a critical task to ensure student success. At present, Brief Motivational Interventions (BMIs) are implemented widely on college campuses but have demonstrated very small effects. Accordingly, if the hypotheses in the present study are confirmed, the Personalized Feedback Program intervention provides a substantial addition to the existing knowledge base concerning interventions for college students. In addition, because the intervention is being implemented during college, potential benefits include the prevention of the severe academic functioning difficulties, including school dropout. Accordingly, developing programming to serve our students will contribute to the Quest for Distinction goal of improving student retention.

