6. * Since a separate protocol document is not uploaded, describe the proposed research using language understandable to those IRB committee members whose expertise is not scientific. The description must include:

- 1. A statement explaining the study design**
- 2. A detailed description of all the procedures that will be followed to carry out the study, preferably in sequential order, and in sufficient detail that the study's methods could be replicated**
- 3. A description of all research measures/tests/interventions that will be used (if applicable)**

See the help text for additional guidance

Study Design: We will conduct a preliminary test of efficacy of our newly developed Personalized Feedback Program through a randomized controlled trial (RCT; target N = 400 freshman college students) comparing four conditions (N = 100 in each): an assessment only treatment as usual control group, Personalized Feedback Program (PFP), a computer-delivered intervention based on brief motivational intervention (BMI) content/principles, and a combined PFP+BMI condition.

Study Procedure:

Generally, participation begins during the Spit for Science baseline survey deployment. At the end of the baseline survey, participants are provided with a brief introduction to this study and asked if they are interested in participation and informed that if they indicate 'yes' that their information will be shared with the study staff so that the staff may contact them to complete study enrollment. The first 400 participants to respond "yes" to this question will be randomly assigned to one of the four conditions outlined below. Based on previous enrollment rates for similar studies, we believe this will allow us to reach our desired sample size of N=300 for each stage of the trial (timepoint).

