Participants will be sent invitations from the study coordinator to their university e-mail account provided on the Spit for Science baseline survey, with an embedded link to participate, which redirects students to the on-line study description and consent. The consent outlines the study procedures for three timepoints: one at the time of initial consent (T1), another 30 days after their initial participation (T2; 1-month follow-up), and a final follow-up approximately 3 months after their initial participation (T3; 3-month follow-up). Upon completion of the on-line consent in REDCap, participants will be redirected to the program to which they were randomly assigned. A description of the procedure at T1 for each condition is outlined below.

Assessment only controls (to participants in this condition, this condition will be called the 'Resources Program'): Upon acceptance of the consent document in REDCap, participants in the control condition will be directed to a REDCap survey. The first page of the survey will consist of a list of resources that they can utilize as a student at VCU containing links to the web pages associated with those resources (details on control group resource content can be found in Description of Measures and Interventions subsection). They will then be asked to answer questions pertaining to their future intentions regarding campus resource use, and alcohol and drug use. They will then be asked to provide their contact information, which will be used to contact them for the remaining follow-up surveys in the study and provide them with their compensation. Once participants complete the survey in REDCap they will automatically be emailed the resource list from the Resources Program should they wish to revisit any information provided. Participation for this group at T1 is expected to take ~10 minutes, but the exact length of time will vary according to how long they spend exploring the website links for the resources provided.

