Approximately 30 days and 3 months post-intervention (post-intervention=after their initial participation at T1), all enrolled participants, regardless of their initial condition, will be invited via email and reminded via email and text by the study coordinator to complete the online Timepoint 2 (T2) and Timepoint 3 (T3) follow-up assessments. All students, regardless of their condition will be directed to the T2 survey at T2 and the T3 survey at T3 via a link in the invitation email and/or text (details on follow-up survey content can be found in Description of Measures and Interventions subsection). At T2, participants will go through the survey, completing all the questions. Upon completion of the survey, participants will be asked to provide their contact information, which will be used to contact them for the remaining follow-up survey in the study and provide them with their compensation. At T3, participants will go through the survey, completing all the questions. Upon completion of the survey, participants will be asked to provide their contact information, which will be used to provide them with their compensation. Each survey is expected to take 15-20 minutes to complete.

Description of Measures and Interventions

Control group resource list: After providing their consent to participate, participants randomly assigned to the treatment as usual control group will be presented with a list of resources available to them as VCU students (e.g. Writing Center, Recreation and Well-Being, Rams Connect), etc. Each resource will link out to its respective web page. The resources listed will match those provided throughout the Personalized Feedback Program (PFP). See attached document "Resources for control group" for full list.

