- Government-generated or collected information that was or will be obtained for nonresearch activities [only applicable to research conducted by or on behalf of a Federal department or agency]
- No secondary data/specimens will be used

Behavioral Intervention Details

1. * Describe the duration of the social/behavioral intervention, task, or environmental manipulation:

The randomized controlled trial (RCT) will compare four conditions:

Assessment only controls will not receive a social/behavioral intervention. They will receive a list of resources at VCU (e.g. Writing Center, Recreation and Well-Being, Rams Connect) with hyperlinks to their respective websites, but they are not required to engage with them in any way.

Personalized Feedback Program (PFP) condition: All participants in this condition will complete the PFP. The PFP is estimated to take approximately 20 minutes, though exact time will depend on the extent to which the participant wishes to engage with each section of the program.

Brief Motivational Intervention (BMI) condition: All participants in this condition will complete a computer-delivered intervention based on BMI content/principles. The BMI is designed to be similar in time to the PFP and is estimated to take approximately 20 minutes to complete.

PFP+BMI condition: All participants in this condition will complete both the PFP and the BMI. The PFP is estimated to take approximately 20 minutes, though exact time will depend on the extent to which the participant wishes to engage with each section of the program. The BMI is designed to be similar in time to the PFP and is estimated to take approximately 20 minutes to complete. Thus the total duration expected is 40 minutes.

2. * Describe any potential harms or discomforts that participants could experience during the intervention:

There is no more than minimal risk associated with participation in this study. Potential risks may be psychological in nature as associated with participation in the Personalized Feedback Program and/or the computer-delivered intervention based on brief motivational intervention content/principles. However, we believe that potential for this kind of distress is minimal. Subjects will be advised to complete the programs only when they have sufficient privacy and they will be reminded regularly that participation is voluntary and they can withdraw from the study at any time during the process.

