One aim of this study is to preliminarily evaluate the efficacy of the Personalized Feedback Program (PFP) in reducing risky substance use among college students as compared to an assessment only control group, a computer-delivered intervention based on brief motivational intervention (BMI) content/principles, and a combined PFP+BMI condition. Thus, the nature of the study requires that we ask participants about their current and past substance use. If we were to share any incidental findings, this could jeopardize the comfort and safety of potential participants to answer the survey honestly.

Risk Benefit Complete

Protocol Progress:

- ➊ INITIAL SETUP
- ➋ BACKGROUND, RATIONALE & GOALS

- ④ RESEARCH PLAN
- ⑤ CONSENT PLAN
- ⑥ RISKS, PRIVACY & CONFIDENTIALITY
- ⑥ POPULATIONS WITH SPECIAL CONSIDERATIONS
- ⑦ INSTITUTIONAL REQUIREMENTS
- ⑧ DOCUMENTS

Click Continue below to go to the next section

View: SF2 - Populations with Special Considerations

Populations with Special Considerations

1. * Check all participant groups that will be either
 - a) Specifically included in this study or
 - b) Discernable in the research data/specimens.

(Selections will branch)

- Children
- Emancipated minors
- Wards of the State
- Pregnant women or fetuses
- Neonates or Post-delivery Materials
- Prisoners
- Decisionally Impaired Adults
- VCU / VCUHS students or trainees
- VCU / VCU Health System employees
- Individuals with limited English proficiency
- Active military personnel
- Student populations in K-12 educational settings or other learning environments
- Members of a federally recognized American Indian and Alaska Native tribe

None of the Above

2. Additional considerations for student populations:

* Select all who will be research participants in the study:

VCU Students

K-12 Students

Parents/Guardians of Students

Teachers

Administrators

Other

3. If applicable, describe any alternative activities for students (including VCU students) who choose not to participate in the research.

4. * Describe how the study will minimize the possibility of coercion to participate.

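### Is the control arm mislabelled as assessment-only, given that controls receive a list of the PFP's campus resources?

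*Protocol*

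**What the plan says.** The aim in Background, Rationale and Goals, Q2, repeated in Study Procedures, Q1, sets the PFP against several comparators, the first being control: "as compared to an assessment only control group". Pertinent and Incidental Findings, Q5, restates the aim as evaluating efficacy "in reducing risky substance use among college students as compared to an assessment only control group". The design statement in Study Procedures, Q6, uses a compound name: "an assessment only treatment as usual control group".

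The control procedures in the same Q6 are specific. At T1, "The first page of the survey will consist of a list of resources that they can utilize as a student at VCU", with links to the relevant web pages. Next, "They will then be asked to answer questions pertaining to their future intentions regarding campus resource use", as well as alcohol and drug use. The list is emailed to them when they finish. Under the measures and interventions, the list is tied to the PFP: "The resources listed will match those provided throughout the Personalized Feedback Program (PFP"). Participants know this arm as the Resources Program, and Compensation, Q1, uses that name too.

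Behavioral Intervention Details, Q1, gives the protocol's own reading of the label: "Assessment only controls will not receive a social/behavioral intervention". Its next sentence says that they get the list "with hyperlinks to their respective websites, but they are not required to engage with them in any way".

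**The concern.** A comparator called assessment-only should receive measurements and nothing more. Here the controls receive campus-resource information, and resource information is one of the routes by which the protocol expects the PFP to help students (Behavioral Intervention Details, Q4). The other three arms receive the PFP, the BMI or both, so no arm meets the literal description.

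Two things could be at stake. First, a null PFP-versus-control result might be reported as showing the PFP to be no better than assessment alone, when the trial has compared it with a resource list. Second, the campus-resource items compare the PFP with a group that has been pointed to the same services. Controls state their T1 intentions straight after seeing the list. If the label led analysts to the wrong contrast, the conclusion drawn for the primary aim would be misworded.

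**Working it through.** No stated figure is in dispute, so the check sets the passages side by side and asks what depends on the label.

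**1. How often the label is used.**
- Statements of what the PFP is compared with: Background Q2, Study Procedures Q1, Pertinent and Incidental Findings Q5. That is 3.
- Design or condition statements: Background Q3; Study Procedures Q2, Q6 (design), Q6 (control condition) and Q7; Behavioral Intervention Details Q1. That is 6.
- Total: 3 + 6 = 9.

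The arm also carries two other names: treatment as usual (twice in Study Procedures, Q6) and Resources Program (Study Procedures, Q6; Compensation, Q1).

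**2. What each side of the PFP-versus-control contrast receives at T1.**

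| Element | Control | PFP |
|---|---|---|
| Campus resources | One untailored linked list, use optional | Recommendations fitted to the student's profile |
| Personality feedback | No | Yes |
| Goal exercises and scenarios | No | Yes |
| Post-program questions | Yes | Yes |
| Material emailed afterwards | The list | The student's results |

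The contrast is therefore feedback, tailoring and interactive content against a generic list. The services named are the same, but the way they are delivered is not. The contrast on resource use still tests whether tailoring helps.

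**3. What depends on the label.**
- *Hypotheses.* Hypothesis 1 compares the PFP with the control condition and with BMI on substance use and related problems. It does not use the label. Hypothesis 2 does not involve the control arm.
- *Sample size.* 4 conditions × 100 = 400, with a desired 300 at each stage. The label enters neither number.
- *Procedures.* The list page, the email and the follow-up surveys are fully described under the label itself.
- *Resource-use items.* These are asked at 3 of 3 timepoints: intentions at T1, utilization at T2 and T3. At T2 and T3 they are additional questions. Neither hypothesis uses them.

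**4. Whether the protocol contradicts itself.** "Assessment only controls will not receive a social/behavioral intervention" would conflict with the list only if the protocol counted the list as a behavioral intervention. It does not. It treats a passive page of services already open to any VCU student as something short of a program, and it says so where the label appears.

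**The case for a change.** The strongest case for a change is that openness in the procedures does not make the wording of the aim accurate. Readers often take the aim from a summary and never reach the procedures. The protocol itself treats the arm as more than measurement: it gives the arm a program name, asks controls how satisfied they were with it, and makes completing it a condition of the T1 payment. The wording would cost almost nothing to change.

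Part of this stands. The label is loose, and three names for one arm is untidy. A report that claimed a comparison with assessment alone would be wrong.

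The rest does not carry the point further. The aim uses a label that the protocol explains elsewhere, and the design statement already qualifies it: "an assessment only treatment as usual control group". The feared misreading needs an author who ignores the description of the arm, which any trial report has to give. It would also be too strong to say that the two groups are given the same thing, because the PFP fits its recommendations to the student's profile. Giving controls the matching list can fairly be read as a way of isolating the personalized content.

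**Conclusion.** The observation is correct, but it is a matter of terminology and calls for no change to the plan. Nine uses of a loose label alter none of the stated figures, arms, procedures or hypotheses. What the controls receive is unambiguous, so analysts will form the right contrast whatever the arm is called. Authors can describe it accurately from the protocol as it stands: the full PFP against a generic, optional resource list.

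This rests on two assumptions. The first is that the substance-use outcomes in the hypotheses carry the efficacy claim, with resource use in a supporting role, as the protocol's wording indicates. The second is that the report describes the control arm by its content. The protocol does not give the size of any effect of the list on substance use. It could be close to zero, and the conclusion does not depend on it, because Hypothesis 1 is stated against the control condition as actually delivered.
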